## 1.2. Study Design

This is an open-label, multicenter, single-arm, interventional study to assess the effect of selexipag in adult participants ( $\geq 18$  to  $< 65$  years) with a diagnosis of PAH up to 52 weeks on study intervention.

The duration of individual participation will be approximately 60 weeks. The study will be conducted in 3 phases: a 28-day screening phase, a 52-week intervention phase (which will include an initial 12-week up-titration period), and a post-intervention safety follow-up period of at least 30 days. Primary and secondary objectives will be evaluated up to Week 26 and exploratory objectives will be evaluated up to Week 52.

The study comprises the following periods:

- **Screening period:** Informed consent signature marks both the start of the study and the start of the screening period.

This period serves to assess eligibility (medical history, treatments, blood tests) and to perform baseline efficacy assessments (MRI, Echo, 6MWD, WHO FC, NT-proBNP, and exploratory blood tests). Screening may last up to 28 days. A participant who is temporarily ineligible may be re-screened. Note: in case MRI, Echo, 6MWT or WHO FC assessment was made as part of routine practice in a way that fully complies with the study requirements, and within 28 days before Day 1, these data can be used for the study.

- **Treatment period:** Starts with the first dose of study drug (Day 1 of study) and ends with EOT on the day of the last dose of the study drug which is at Week  $52 \pm 7$  days or at premature discontinuation of study intervention. This period includes:
  - **Day 1:** Day 1 is defined as the day when a participant receives the first dose of study intervention. First dosing should occur at the site. Day 1 may occur once screening assessments are completed, and no later than 28 days after informed consent signature. For re-screened participants, all screening assessments must have been made (or repeated) within 28 days before Day 1.
  - **Up-titration:** During this period, study intervention will be up-titrated from Day 1 to the end of Week 12 (Day 84). Weekly phone calls from the site to participant will be performed to guide the up-titration and collect safety information. At the end of Week 4 (+ 7 days) and Week 12 (+ 7 days) and participants will return to the site for a return/dispensing visit; no assessments will be performed at these site visits.

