### **5.6.1. Extent of Exposure**

Exposure will be summarized up to EOT.

The number and percentage of participants who received study intervention will be summarized.

Descriptive statistics for duration of study intervention (N, mean, SD, median, and range (minimum, maximum)) will be summarized. Participant-years of intervention are calculated as [days of intervention/365.25].

Duration of exposure will be summarized in the following duration categories: <1 week, 1-<4 weeks, 4-<12 weeks, 12-<26 weeks,  $\geq$  26 weeks.

Cumulative duration of intervention  $\geq$  1 week,  $\geq$  4 weeks,  $\geq$  12 weeks,  $\geq$  26 weeks will be summarized.

Study intervention duration is defined as (date of last dose of study intervention – date of first dose of study intervention) +1.

Total dose days of intervention is defined as the total number of days that study intervention was administered to the participant (excluding days off study intervention).

The number (%) of participants with a dose adjustment/dose not administered will be summarized. Reasons for dose adjustments/doses not administered will also be summarized.

Descriptive statistics will be presented for the following parameters during the dose maintenance period:

- The number (%) of participants with a dose adjustment after the 12-week up-titration period. Reasons for dose adjustments will also be summarized.
- Cumulative total dose per participants
- Mean daily dose per participant (after the 12-week up-titration period)
- IMD at end of Week 12 (Day 84).

The mean daily dose of study intervention is calculated as (sum of total daily dose)/study treatment duration.

The total daily dose is calculated according to frequency and dose ( $\mu$ g).

Frequency (coded) a	Total daily dose (µg / day)
Once a day	dose
Twice a day	2 × dose
Twice weekly	2 × dose / 7
Monthly	dose / 30.5
Every other day	dose / 2
<X> times	<X> × dose
<X> times	<X> × dose / 7
Weekly	dose / 7
Every <X>	dose /(7 × <X>)
Twice per month	2 x dose / 30.5
Missing, other codes	0

a: values coded to CONTINUOUS, ONCE, AS NECESSARY, INFREQUENT, UNKNOWN cannot be used to determine the total daily dose and therefore the total daily dose will be set to zero.

The cumulative total dose per participant is calculated as the sum of total daily dose over the whole treatment period.

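### SAP 5.6.1 lists cumulative total dose under the maintenance period but defines it over the whole treatment period, and the mean daily dose formula does not match its post-titration label

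*SAP*

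**What the plan says.** SAP 5.6.1 introduces four dose summaries with the words "Descriptive statistics will be presented for the following parameters during the dose maintenance period". The second item is "Cumulative total dose per participants", which carries no period of its own. The third is "Mean daily dose per participant (after the 12-week up-titration period", which does.

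The formulas follow lower in the same section. For the mean: "The mean daily dose of study intervention is calculated as (sum of total daily dose)/study treatment duration". For the cumulative dose: "The cumulative total dose per participant is calculated as the sum of total daily dose over the whole treatment period".

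Other definitions bear on these:

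- SAP 1.2 defines the treatment period: "Starts with the first dose of study drug (Day 1 of study) and ends with EOT on the day of the last dose". It therefore includes up-titration.
- SAP 5.6.1 defines one duration: "Study intervention duration is defined as (date of last dose of study intervention", less the date of first dose, plus one day.
- SAP 5.1.6 starts maintenance on the day after the Week 12 visit, for participants who had not discontinued by then. SAP 5.1.7 ends it at the end-of-treatment date or death, with the end-of-trial date as fallback. The mean daily dose formula refers to neither section.
- A footnote to the frequency table says that certain codes (for example, as necessary or unknown) "cannot be used to determine the total daily dose and therefore the total daily dose will be set to zero".

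**The concern.** The list heading and the definition give cumulative total dose two different periods, and they cannot both hold. If the definition is followed, the table shows a maintenance-period figure that contains the up-titration doses.

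For mean daily dose, the label fixes the period as post-titration, but the formula does not carry that period into either term. The denominator is not worded exactly as any defined term. Its nearest match is the first-to-last-dose duration, which conflicts with the label. Two programmers could follow the text in good faith and report different means.

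Selexipag is titrated individually, so these summaries are how a reader learns what exposure was reached in maintenance. SAP 5.1 reduces efficacy to listings and keeps the usual tables for safety, so exposure is among the few outputs still summarised.

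A secondary matter is the footnote, which records an unknown dose as a known zero. If drug was taken on those days, both summaries are biased downward.

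**Working it through.** The SAP states no exposure figure, so there is none to reproduce. The example below shows the size of the difference.

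**Inputs**

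- Titration: Protocol Table 2, rising by 200 µg twice daily each week. For an individual maintenance dose (IMD) of 1,600 µg, that dose is reached in Week 8 and held.
- Day 1: one dose only (Table 2, footnote a).
- IMD range: 200 to 1,600 µg twice daily (Protocol 6.2.1).
- Maintenance start: the day after the Week 12 visit (SAP 5.1.6). With the visit on Day 84 and a +7-day window (SAP 1.2), this is Day 85 to Day 92.
- Treatment length T: 364 days as planned; 182 days as an assumed shorter case.
- Assumptions: no interruptions and full doses from Day 2. Taking each new dose first in the evening would remove about 7 × 200 = 1,400 µg, or 0.1% of the total, and is ignored.

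**Cumulative dose, IMD 1,600 µg twice daily**

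- Dose to Day 84 = 2 × 7 × (200 + 400 + … + 1,600) − 200 + 28 × 3,200 = 100,600 + 89,600 = 190,200 µg.
- Whole period, T = 364: 190,200 + 280 × 3,200 = 1,086,200 µg.
- Maintenance only: 280 × 3,200 = 896,000 µg (start Day 85) or 273 × 3,200 = 873,600 µg (start Day 92).
- Ratio 1.21 to 1.24; gap 190,200 to 212,600 µg.
- T = 182: whole period 503,800 µg against 313,600 or 291,200 µg; ratio 1.61 to 1.73. At a given IMD the gap is unchanged, but the ratio grows as treatment shortens.

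**Cumulative dose, IMD 200 µg twice daily, Week 12 visit on Day 84**

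- Dose to Day 84, which is the gap = 84 × 400 − 200 = 33,400 µg.
- T = 364: 33,400 + 112,000 = 145,400 µg against 112,000 µg; ratio 1.30.

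**Mean daily dose at T = 364 (µg/day)**

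| Sum | Divided by | IMD 1,600 twice daily (taken: 3,200) | IMD 200 twice daily (taken: 400) |
|---|---|---|---|
| Maintenance | Maintenance days | 3,200 (0%) | 400 (0%) |
| Maintenance, start Day 85 | First to last dose, 364 | 896,000/364 = 2,462 (−23%) | 112,000/364 = 308 (−23%) |
| Maintenance, start Day 92 | First to last dose, 364 | 873,600/364 = 2,400 (−25%) | 109,200/364 = 300 (−25%) |
| Whole period | First to last dose, 364 | 1,086,200/364 = 2,984 (−7%) | 145,400/364 = 399.5 (−0.1%) |

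The error in the second and third rows equals the up-titration share of treatment, 84/364 or 91/364, so it does not depend on IMD. The error in the last row does.

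**Who is counted.** A participant on the top schedule who stops on Day 60 has a whole-period total of 100,600 + 4 × 3,200 = 113,400 µg but no maintenance period. The choice of period therefore also changes the number of participants summarised.

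**Zero coding.** If k of n maintenance days carry an unusable code and the dose taken is constant, the mean falls by k/n. The documents give no rate. As an assumed range, 3/280 = 1% and 28/280 = 10%.

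**The case against.** The strongest reply is that this is a labelling fault and the intent can be recovered. The cumulative dose definition is explicit and gives one programmable result. The list heading is loose in any case, since its last item, the IMD at the end of Week 12 on Day 84, precedes the maintenance start in SAP 5.1.6. For the mean, the bullet states the period, SAP 5.1.6 and 5.1.7 supply the dates, and the matched calculation gives no error. All of this stands. It makes the remedy simple, but the heading and the definition still disagree, and the formula still omits the period that the bullet gives.

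A reader might infer that the mean is divided by an undefined duration. The documents do not support that. SAP 5.6.1 defines a study intervention duration a few lines earlier, SAP 5.1.8 uses study treatment for the same drug, and Protocol Section 2 equates study intervention with study drug. The fault is that the natural reading of the denominator conflicts with the label.

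On zero coding, the rule is explicit and reproducible, and the protocol's once-daily and twice-daily regimens are both codable. Few days should be affected, so this stays secondary.

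**Conclusion.** The point holds and is minor. Cumulative total dose is given two incompatible periods. On the schedule assumed here, the figure as defined exceeds the maintenance-only figure by a factor of 1.21 to 1.24 at 364 days for an IMD of 1,600 µg twice daily, and by 1.30 for 200 µg with a Day 84 visit. The mean daily dose formula, read naturally, conflicts with its own label. The result is 23% to 25% too low if only the sum is restricted to maintenance. If neither term is restricted, it is 7% too low at the top IMD and about 0.1% too low at the lowest.

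Two stronger inferences should be resisted. The −23% to −25% is not an expected error: it arises only if the label is applied to the numerator and ignored in the denominator. The 190,200 µg gap and the −7% belong to the top IMD and do not describe every participant. Nor is any efficacy result affected; the consequence stops at descriptive exposure tables in a prematurely terminated study with very few participants.

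**What to change.** 1. Move cumulative total dose out of the maintenance list and label it as covering the whole treatment period. If a maintenance figure is also wanted, add it as a separate item.
2. Compute mean daily dose with numerator and denominator both running from the maintenance start in SAP 5.1.6 to the maintenance end in SAP 5.1.7 or the last dose, whichever is earlier. The cap matters mainly where the end-of-trial fallback would add days off drug. Replace the duration term in the formula with this stated period.
3. State that participants who stopped before Week 12 have no maintenance value, and show the number summarised.
4. Treat frequency codes still unresolved after data queries as missing, leave those days out of both terms of the mean, and report how many days and participants are affected.

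The cost is a few lines of SAP wording and one derivation in a descriptive table. The dates are already defined and no new data are needed.

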### 5.6.2. Adverse Events

The verbatim terms used in the CRF by investigators to identify adverse events will be coded using the Medical Dictionary for Regulatory Activities (MedDRA). Any AE occurring at or after the initial administration of study intervention through the day of last dose plus 3 days is considered to be treatment-emergent. If the event occurs on the day of the initial administration of study intervention, and either event time or time of administration are missing, then the event will be assumed to be treatment emergent. If the event date is recorded as partial or completely missing, then the event will be considered to be treatment emergent unless it is known to be prior to the first administration of study intervention based on partial onset date or resolution date. All reported treatment-emergent adverse events will be included in the analysis. For each adverse event, the number and percentage of participants who experience at least 1 occurrence of the given event will be summarized.

Note: for participants who are entering another open-label clinical study with selexipag, safety information will be reported up to the last dose in RESTORE as the EOT visit will be combined with EOS visit. This is intended to avoid duplicate reporting of adverse events (AEs).

Summary tables will be provided for treatment-emergent adverse events by System Organ Class (SOC) and Preferred Term (PT):

- AEs
- Serious AEs (SAEs)

- AEs leading to discontinuation of study intervention
- AEs of COVID-19
- AEs by severity
- AEs by relationship to study intervention

SAEs will also be tabulated up to 30 days after end of study intervention or EOS whichever is first. In addition to the summary tables, listings will be provided for participants who:

- Had AEs
- Had SAEs
- Had AEs leading to discontinuation of study intervention
- Had AEs of special interest (AESI) (see [Appendix 8](#))

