8.5. Adverse Events, Serious Adverse Events, and Other Safety Reporting

Timely, accurate, and complete reporting and analysis of safety information, from clinical studies are crucial for the protection of participants, investigators, and the sponsor, and are mandated by regulatory agencies worldwide. The sponsor has established standard operating procedures in conformity with regulatory requirements worldwide to ensure appropriate reporting of safety information; all clinical studies conducted by the sponsor or its affiliates will be conducted in accordance with those procedures.

AEs will be reported by the participant (or, when appropriate, by a caregiver, surrogate, or the participant's legally acceptable representative) for the duration of the study.

Further details on AEs, SAEs, and PQC can be found in Section [10.4](#).

8.5.1. Time Period and Frequency for Collecting Adverse Event and Serious Adverse Event Information

All Adverse Events

All AEs and special reporting situations (Section 10.4), whether serious or non-serious, will be reported on specific Adverse Event pages of the eCRF throughout the study from signing of the ICF onwards until the EOS visit (see Section 4.4) or date of last contact (see Section 7.3).

Serious Adverse Events

All SAEs, as well as PQC, occurring during the study must be reported to the appropriate sponsor contact person by study-site personnel within 24 hours of their knowledge of the event.

Serious adverse events, including those spontaneously reported to the investigator until EOS, must be reported on Adverse Event pages in the eCRF and on the Serious Adverse Event form, whether or not this event is considered by the investigator to be related to study intervention.

Information regarding SAEs will be transmitted to the sponsor using the Serious Adverse Event form, which must be completed and signed by a physician from the study site, and transmitted to the sponsor immediately but no later than within 24 hours. The initial and follow-up reports of a SAE should be made by facsimile (fax) or email. Telephone reporting should be the exception and the reporter should be asked to complete the appropriate form(s) first.

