9.4.5. Safety Analyses

Safety analyses will be performed on the SS.

Adverse Events

A treatment-emergent AE is any AE from first dose up to 3 days after end of study intervention. The number and percentage of participants experiencing at least 1 treatment-emergent AE or SAE will be tabulated by:

- Medical Dictionary for Regulatory Activities system organ class and individual preferred term, in descending order of incidence.
- Frequency of participants with events coded with the same preferred term, in descending order of incidence.

Furthermore, treatment-emergent AEs and SAEs will be tabulated as described above by severity and relationship to study intervention. SAEs will be also tabulated up to 30 days after end of study intervention.

AEs leading to premature discontinuation of study intervention, AEs with an outcome of death, and AEs of special interest will be summarized as described above. The detailed list of AEs of special interest will be specified in the SAP.

AEs occurring during titration period will also be summarized separately.

Listings will be provided for all reported AEs, including SAEs. In addition, separate listings, as well as narratives, will be provided for SAEs, for AEs leading to premature discontinuation of study intervention, and for AEs with an outcome of death.

The following AEs will be listed only:

- AEs occurring prior to first study intervention dose
- Non-serious AEs occurring after EOT + 3 days
- SAEs occurring more than 30 days after discontinuation of study intervention

Clinical Laboratory Tests

Descriptive summary statistics by visit will be provided for observed values and absolute changes from baseline, in both hematology and clinical chemistry laboratory tests. In order to minimize missing data and to allow for out-of-window visits, all recorded assessments up to EOT + 3 days will be assigned to the most appropriate visit timepoint according to the best fitting time window for that assessment.

The sponsor's internal guidelines will be used for the definitions of marked abnormalities and for the standardization of numeric values obtained from different laboratories and/or using different normal ranges. Standard numeric laboratory variables will be transformed to standard units. All laboratory data transferred will be taken into account regardless of whether they correspond to scheduled (per protocol) or unscheduled assessments.

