### **5.1.8. Imputation Rules for Missing AE Date/Time of Onset/Resolution**

Partial AE onset dates will be imputed as follows:

- If the onset date of an adverse event is missing day only, it will be set to:
  - First day of the month that the AE occurred, if month/year of the onset of AE is different than the month/year of the first dose of study treatment.
  - The day of first dose of study treatment, if the month/year of the onset of AE is the same as month/year of the first dose of study treatment and month/year of the AE resolution date is different
  - The day of first dose of study treatment or day of AE resolution date, whichever is earliest, if month/year of the onset of AE and month/year of the first dose of study treatment date and month/year of the AE resolution date are same.
- If the onset date of an adverse event is missing both day and month, it will be set to the earliest of:
  - January 1 of the year of onset, as long as this date is on or after the first dose of study treatment
  - Month and day of the first dose of study treatment, if this date is the same year that the AE occurred
  - Last day of the year if the year of the AE onset is prior to the year of the first dose of study treatment,
  - The AE resolution date.
- Completely missing onset dates will not be imputed, but the event will be assumed to be treatment emergent unless otherwise indicated.

Partial AE resolution dates not marked as ongoing will be imputed as follows:

- If the resolution date of an adverse event is missing day only, it will be set to the earliest of the last day of the month of occurrence of resolution or the day of the date of death, if the death occurred in that month.
- If the resolution date of an adverse event is missing both day and month, it will be set to the earliest of December 31 of the year or the day and month of the date of death, if the death occurred in that year.
- Completely missing resolution dates will not be imputed.

Concomitant therapy start dates will be imputed as follows:

- If the start date is missing day only, it will be set to first day of the month.
- If the start date has the year, but is missing the month, it will be set to January 1.
- If the start date is completely missing, it will not be imputed.

Concomitant therapy end dates will be imputed as follows:

- If the start date is missing day only, it will be set to last day of the month.

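### The SAP counts an adverse event with a partial onset date as treatment-emergent even when that date proves onset after the window of last dose plus 3 days

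*SAP*

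**What the plan says.** SAP Section 5.6.2 bounds the treatment-emergent period on both sides. An event qualifies from first administration "through the day of last dose plus 3 days is considered to be treatment-emergent". The same paragraph then gives a default for any event whose date is incomplete or absent: "then the event will be considered to be treatment emergent unless it is known to be prior to the first administration of study intervention", judged from the partial onset date or the resolution date. That is the only exception.

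SAP Section 5.1.8 imputes partial onset dates. When only the day is missing, the rule is "First day of the month that the AE occurred, if month/year of the onset of AE is different than" the month of first dose. It presumes emergence in one situation only: "Completely missing onset dates will not be imputed, but the event will be assumed to be treatment emergent unless otherwise indicated".

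Protocol Section 9.4.5 uses the same 3-day window and names "Non-serious AEs occurring after EOT + 3 days" among the events to be listed and not tabulated. Protocol Section 8.5.1 has adverse events recorded "throughout the study from signing of the ICF onwards until the EOS visit". Protocol Section 4.4 places that visit at least 30 days after last dose, except for participants who move to another open-label selexipag study, whose end-of-study visit is the end-of-treatment visit.

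**The concern.** The partial-date rule respects what an incomplete date proves at the start of the window and ignores what it proves at the end. Events after last dose plus 3 days are collected, because follow-up lasts at least 30 days for participants who do not roll over. Some of them may have an onset date without a day.

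Read literally, Section 5.6.2 puts such an event in the treatment-emergent tables even when the recorded month begins after the window has closed. That contradicts the section's own window and the protocol's listed-only rule. SAP Appendix 2, which sets out changes to the protocol's analyses, mentions no such change. It also gives a different answer from Section 5.1.8, and no sentence says which section governs. Two programmers could each follow the SAP and deliver different tables.

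After early termination SAP Section 5.1 reduces efficacy to listings, so the safety tables are among the few summaries left.

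**Working it through.** **Inputs.** Window end: last dose + 3 days (SAP 5.6.2; Protocol 9.4.5). Day-missing onset in a month other than the first-dose month: imputed to the first of that month (SAP 5.1.8). Collection: to end of study, at least 30 days after last dose unless the participant rolls over (Protocol 8.5.1 and 4.4). The plan gives no figure on this point to reproduce.

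**One event, followed through each rule.** The dates are illustrative: last dose 10 May, onset recorded as June with no day.

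| Rule | Step | Classification |
|---|---|---|
| Window in SAP 5.6.2 | closes 13 May; earliest possible onset is 1 June | not treatment-emergent |
| Imputation in SAP 5.1.8 | 1 June is later than 13 May | not treatment-emergent |
| Protocol 9.4.5, if non-serious | after end of treatment + 3 days | listed only |
| Partial-date rule in SAP 5.6.2 | not known to precede first dose | treatment-emergent |

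The last row stands alone. It cannot be dismissed as superseded by imputation, because it is triggered by the date as recorded.

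**How often a month-only date settles the matter.** Assume last-dose dates spread evenly over 365 days and true onset uniform over a stated range of days *d* after last dose. The date proves late onset when the first day of the onset month, *F*, is later than last dose + 3 and no later than last dose + *d*. For each *F* that leaves the last-dose dates from *F* − *d* to *F* − 4, which is *d* − 3 dates. With 12 month starts:

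share = 12 × Σ(*d* − 3) / (365 × number of onset days)

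- Days 4–7: 12 × 10 / (365 × 4) = 120/1460 = 8%
- Days 4–14: 12 × 66 / (365 × 11) = 792/4015 = 20%
- Days 4–30: 12 × 378 / (365 × 27) = 4536/9855 = 46%
- Days 15–30: 12 × 312 / (365 × 16) = 3744/5840 = 64%

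**Sensitivity to when dosing ends.** For onset on Days 4–30 and a single last-dose date, the share is 0% for 1 May or 31 May, 33% (9 of 27) for 10 May, and 100% for 28 May.

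**Effect of one event.** Adding one participant to a preferred term changes its incidence by 1/n. With n assumed to be 10 to 20, that is 1/10 = 10 points to 1/20 = 5 points. This is an upper case, because the table moves only if that participant has no on-treatment occurrence of the same term.

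**The case against.** The strongest reply is that a sensible analyst would impute under Section 5.1.8 first and then apply the window, which gives the intended answer. On that view the fault is an unstated order of rules. This reading is reasonable, but the text does not require it: the Section 5.6.2 rule acts on the recorded date, and nothing gives the imputed date priority.

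A second reply is that defaulting to treatment-emergent is cautious, since it over-counts and hides nothing. That justifies the default when timing is uncertain. It does not justify counting an event whose recorded month lies wholly outside the window.

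A third reply is that the case is rare. It needs a participant who does not roll over, a new event after the window, an onset day still missing after queries, a recorded month that starts after the window, and no on-treatment occurrence of the same term. The documents show no such event. The calendar shares are conditional on a month-only follow-up event existing, and they range from 0% to 100% if last doses cluster, as they may in a study stopped early. All of this stands. It limits the size of the problem and leaves the misclassification in place.

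For serious events the effect is smaller still, because "SAEs will also be tabulated up to 30 days after end of study intervention or EOS whichever is first". A serious event after the 3-day window but within that limit is tabulated in any case; only its place in the treatment-emergent table changes.

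**Conclusion.** The concern holds. The partial-date rule in SAP Section 5.6.2 gives a wrong classification for an event whose partial onset date proves it began more than 3 days after last dose, and it conflicts with SAP Section 5.1.8 and Protocol Section 9.4.5. It should be corrected, but the consequence is small: possible inflation of descriptive treatment-emergent counts in a single-arm study with no remaining hypothesis test and with individual events listed. Roll-over participants are unaffected, because their "safety information will be reported up to the last dose in RESTORE".

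The textual conclusion needs no assumption. The practical size is unknown, since the documents report neither the number of partial dates nor an onset distribution. The 8% to 64% shares depend on evenly spread last-dose dates and uniform onset, and show only that the case is plausible. The 10 to 5 point step depends on an assumed 10 to 20 treated participants; SAP Section 5.3.2 says only that numbers are very limited.

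**What to change.** In SAP Section 5.6.2, extend the exception so that it covers both ends of the window:

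> …unless the partial onset date or the resolution date shows that the event began before first dosing, or the partial onset date shows that it began more than 3 days after the last dose.

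The second limb uses the onset date only, because a late resolution date does not show when an event began. An event whose recorded month overlaps the window stays treatment-emergent, so the cautious default remains wherever timing is uncertain. For day-missing onset dates after the window, Sections 5.6.2 and 5.1.8 then agree, so the example no longer depends on which is applied first.

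Do not carry the 3-day wording into the separate serious-event table. If a partial-date rule is wanted there, its limit is the one that table already has: 30 days after the end of study intervention or end of study, whichever comes first.

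Cost: one clause in the SAP and one condition in the treatment-emergent flag. No new data are needed.
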